1. PURPOSE OF THE STUDY

a. Brief Summary

The purpose of the study is to develop a cognitive training method that is short, effective and engaging.

b. Objectives

We hope to learn how NIRS-based neurofeedback enhance the effectiveness of cognitive training.

c. Rationale for Research in Humans

The purpose of this study is to examine how human subjects can control their cognitive functions using real-time neurofeedback.

2. STUDY PROCEDURES

a. Procedures

Trained students and staff will screen, consent, enroll, assess, and monitor participants through every step of the process.

Neuroimaging includes functional MRI, anatomical MRI, and NIRS. Participant's physiological responses including heart rate and breathing rate, may be measured inside and/or outside of an MRI scan. This may require a belt around the chest or abdomen (to measure respiration), a pulse oximeter to be worn on the finger. Wearable or standalone eye-tracking devices may be used to track participant's eye movement pattern during the training. Participant's head movement will be recorded during NIRS measurements using an accelerometer in order to improve the quality of neurofeedback.

VR googles may be used for presenting computerized tasks and/or training.

Demographic data will be collected including education level, ethnicity, socioeconomic status and occupational history. Neuropsychological testing includes measures of IQ, executive functioning, memory, language processing and visual-motor integration. We will also include the Tanner staging assessment - which is a self report scale of physical development to assess where the child is in terms of puberty. Psychiatric assessment will also be done to assess for current and previous emotional and behavioral problems.

Participants will undergo the following procedures:

- 1) Screening: Potential subjects will be screened via telephone interview (see attached Screen document) or email questionnaire (see eScreen). The screening will involve only questions relevant to this study including certain demographic information, medical and developmental history to establish eligibility status.
- 2) Consent: All eligible participants will undergo informed consent procedures.
- 3) Neuropsychological Assessment: All participants will be administered a battery of standardized neuropsychological tests as stated above.
- 4) NIRS and MRI measurements: Participants will undergo functional near- infrared spectroscopy (NIRS) and magnetic resonance imaging (MRI) measurements. No injections or other invasive procedures will be utilized. NIRS and MRI will be used to provide subjects with real-time feedback about their brain activity during cognitive training as well as to measure the participants' brain activity.
- 5) Intervention: All participants will either undergo cognitive training with neurofeedback via NIRS or be waitlisted. Participants will have 50% chance to undergo the cognitive training with neurofeedback; those in the waitlist group have the option to receive complimentary cognitive training with neurofeedback after completion of the study.

b. Procedure Risks

Neuropsychological assessment is a very low risk procedure and represents the only objective, valid and reliable method for accurately measuring cognitive function in humans. Neuropsychological assessment represents the standard of care for diagnosing cognitive impairments in children and adults.

Neuroimaging assessments using magnetic resonance imaging scans and NIRS are the most accurate and non-invasive, low-risk methods for determining neurobiological function in humans. Near-Infrared Spectroscopy has the additional benefit of not requiring the subject to endure loud noises or confined space for any period of time. This study will not employ any invasive neuroimaging techniques such as injection of contrast agents. MRI scans and NIRS measurements represent the only existing methods for obtaining accurate, *in vivo* measurements of the human brain.

c. Use of Deception in the Study

N/A

d. Use of Audio and Video Recordings

Video recording will occur. We will archive the data on the CIBSR server, which is housed in the CIBSR facility in the Department of Psychiatry and Behavioral Sciences. We will occasionally use images or footage in scientific presentations, but in such instances all identifying information will be eliminated or occluded. In such presentations, the recordings will be used to demonstrate the nature of the task and of our study procedure. The recordings will remain on the CIBSR secure server in archived form.

e. Alternative Procedures or Courses of Treatment

N/A

f. Will it be possible to continue the more (most) appropriate therapy for the participant(s) after the conclusion of the study?

N/A There are no treatments involved.

g. Study Endpoint(s)

N/A There are no treatments involved.

3. BACKGROUND

a. Past Experimental and/or Clinical Findings

Cognitive training is an emergent approach for interrogating brain systems and mechanisms (such as neuroplasticity) that are associated with certain cognitive skills and the practice of cognitive skills. Cognitive training promotes several neuroplastic mechanisms in the brain and has been shown to improve cognitive functioning in healthy individuals. While the mechanism underlying these plasticity- related changes in the brain is still unclear, it is speculated that cognitive training enhances individual's cognitive reserve (i.e. brain's ability to perform cognitive tasks) by recruiting either an alternative brain network or through a more efficient utilization of brain networks.

The main goal of cognitive training is to boost a specific cognitive ability/brain mechanism by employing a set of cognitive training paradigms that target a specific cognitive function. In order for the cognitive training to be effective, individuals are usually asked to perform a set of cognitive training paradigms for a long period of time (1 to 6 months, 10 to 300 hours). The question that we arise here is whether we can make a more efficient cognitive training program that is short and effective. This will be realized by designing a training program that assures subjects will use the targeted brain regions during the training.

b. Findings from Past Animal Experiments

Other groups have shown that cognitive training enhances brain activity in animals.

4. DEVICES USED IN THE STUDY

a. Investigational Devices (Including Commercial Devices Used Off-Label)

Investigational Device 1	
Name:	Customized MRI Scan Equipment
Description:	Some of the RF imaging coils, imaging software and other devices used to conduct scans at the Lucas Center and CNI (Stanford Center for Cognitive and Neurobiological Imaging) are not approved by the FDA.
Significant Risk? (Y/N)	No
Rationale for Non-Significant Risk	The customized equipment does not currently exist in the market, hence our characterization of it as investigational. However, it has been tested for safety by highly trained Lucas personnel.
Investigational Device 2	
Name:	W-NIRS
Description:	An investigational, custom-built NIRS system that is wearable/portable and more cost-effective than commercially available NIRS systems. The engineering collaborator moved from Stanford to Vanderbilt and they keep providing with next iterations of the device. Vanderbilt will not be involved in our study and they will not receive data collected at Stanford.
Significant Risk? (Y/N)	No
Rationale for Non-Significant Risk	There is no known risk associated with functional NIRS. The LED sources used in the system operate under IEC/ANSI standards. These LEDs expose participants to much less light compared with commercially available laser-based NIRS systems.

b. IDE-Exempt Devices

IND-Exempt Device 1	
Name:	ETG-4000 (Hitachi)
Description:	NIRS technology uses specific wavelengths of light, introduced at the scalp, to enable the noninvasive measurement of changes in the relative ratios of deoxygenated hemoglobin (deoxy-Hb) and oxygenated hemoglobin (oxy-Hb) in the capillary beds during brain activity.
IND-Exempt Device 2	
Name:	NIRSSport (NIRx Medical Technologies)
Description:	NIRS technology uses specific wavelengths of light, introduced at the scalp, to enable the noninvasive measurement of changes in the relative ratios of deoxygenated hemoglobin (deoxy-Hb) and oxygenated hemoglobin (oxy-Hb) in the capillary beds during brain activity.
IND-Exempt Device 3	
Name:	ETG 2.0 (SMI)
Description:	SMI Eye Tracking Glasses 2 Wireless (SMI ETG 2w) are a glasses-type eye tracker with full wireless control and live annotations. Instant calibrationless setup and 4+hrs mobile operation with the SMI ETG 2w smart recorder ensure outstanding productivity for mobile eye tracking research.
IND-Exempt Device 4	
Name:	VIVE (HTC)
Description:	Commercially available VR Goggles and related cameras for presenting the computerized exercises/games in an immersive VR environment.
IND-Exempt Device 5	
Name:	Gear VR
Description:	Commercially available VR Goggles and related cameras for presenting the computerized exercises/games in an immersive VR environment.
IND-Exempt Device 6	
Name:	NIR Scout (NIRx Medical Technologies)
Description:	NIRS technology uses specific wavelengths of light, introduced at the scalp, to enable the noninvasive measurement of changes in the relative ratios of deoxygenated hemoglobin (deoxy-Hb) and oxygenated hemoglobin (oxy-Hb) in the capillary beds during brain activity.

5. PARTICIPANT POPULATION

a. Planned Enrollment

This research study is looking for 160 participants with ADHD.

b. Age, Gender, and Ethnic Background

Participants (males and females) ages 7-11 years of all ethnic backgrounds will be recruited.

c. Vulnerable Populations

We have already tested the efficacy of the proposed cognitive training in healthy young adults in previous phases of the study. We will be studying minors because, in the future, neurofeedback and cognitive control paradigms are likely to benefit still-developing minors most, due to the increased plasticity associated with early neurodevelopmental processes. Thus, we hope to specifically address the applicability of neurofeedback scenarios in developing populations. We will be taking special precautions to protect the rights of these minors, including following well-established protocols for parental consent and assent.

d. Rationale for Exclusion of Certain Populations

N/A

e. Stanford Populations

Laboratory personnel and students may be subjects in piloting phases.

f. Healthy Volunteers

Participants will be children with ADHD.

Parents and subjects will be asked to notify research staff immediately if they encounter any problems and participation can be discontinued at any time..

g. Recruitment Details

Subjects will be identified using established recruitment measures used at the Center for Interdisciplinary Brain Sciences Research. These procedures include advertising online, including on ResearchMatch, or in local newspapers and posting notices in public places. These procedures also include email messages to email lists and to potential participants.

h. Eligibility Criteria

i. Inclusion Criteria

Meeting diagnostic criteria for ADHD, determined by a BRIEF Working Memory score ≥ 65 . Age range: 7 years - 11 years.

ii. Exclusion Criteria

Presence of contraindications for MRI (orthodontia, vascular stents, metallic ear tubes, metal implants, pregnancy, etc) for those participating in an MRI scan. History of serious medical, neurological or psychiatric illness (except disorders of interest) or sensory impairment.

i. Screening Procedures

Potential participants will be screened for inclusion and exclusion criteria via an online and/or telephone screen (see attachments). Only information necessary to ascertain eligibility will be requested. Because the screening will include questions involving medical history to determine diagnosis of ADHD, a limited waiver of authorization will be requested in section 15.

j. Participation in Multiple Protocols

The screening questionnaire will include a question regarding other study participation. Participants can be enrolled in other studies that do not involve medications or substances which would affect the MRI and NIRS measurements or cognitive interventions. Each case will be evaluated individually prior to enrollment.

k. Payments to Participants

Participants will be provided with up to \$300 for their participation. If the participant does not complete the all study visits, he will be reimbursed \$20/hr for the portion of the study that he has completed.

l. Costs to Participants

None

m. Planned Duration of the Study

The study will require approximately 5 years to complete. Total time per participant: 10-15 minutes for screening, 30 minutes for consent, 30-60 minutes for each neuropsychological testing session, 1 hour for NIRS (or MRI) measurements. Analysis of participant data will require approximately 18 hours per participant.

6. RISKS

a. Potential Risks

i. Investigational devices

For MRI scans, there is a minimal non-significant risk associated with use of the custom-developed imaging coils, imaging software and other non-FDA approved devices used at the Lucas Center.

For NIRS scans, there is also a minimal non-significant risk associated with the use of a custom-developed cap for holding infrared optodes in place.

ii. Investigational drugs

N/A

iii. Commercially available drugs, biologics, reagents or chemicals

N/A

iv. Procedures

Neuropsychological testing
NIRS measurements
MRI measurements
Eye Tracking
VR-based cognitive assessments and training

v. Radioisotopes/radiation-producing machines

N/A

vi. Physical well-being

See notes about MRI and NIRS risks above. Otherwise N/A

vii. Psychological well-being

There is a slight risk that subjects will experience some anxiety, frustration or distress during the neuropsychological testing and/or NIRS/MRI procedures. However, this will be minimized by training and preparation by clinicians. Any anxiety or distress will be brief and transient and the neuropsychological testing will involve rest breaks to minimize discomfort and the NIRS/MRI measurements can be stopped at any time by the participant.

viii. Economic well-being

There is no known risk to subjects' economic well being.

ix. Social well-being

There is no known risk to subjects' social well being.

x. Overall evaluation of risk

Low

b. International Research Risk Procedures

N/A

c. Procedures to Minimize Risk

The consent form for all participants lists all possible risks of the procedures. Research staff administering neuropsychological testing will be trained in clinical assessment including how to recognize and deal appropriately with participant distress. Frequent rest breaks will be included in the assessment protocol to help minimize frustration, fatigue and distress.

Research staff are well trained to use protocols and procedures to ensure that the NIRS and MRI equipments are used correctly to minimize any risks. Subjects are instructed that

they can alert the operator that they need help or need to ask a question by speaking directly to the experimenter during the NIRS/MRI scan.

All data handling procedures will follow HIPAA regulations. For each participant, a folder is created that contains signed consent forms, screening questionnaires and NIRS/MRI logs. This folder serves as a permanent archive of original participant data. Extensive precautions are taken to insure the privacy of participants and the confidentiality of data. Specifically, participant identity is numerically coded on all pages within data folders and in the database. All data folders are kept in confidential, locked files at Stanford University. Only personnel directly associated with the grant have access to these files. Data are entered into the computerized database using only the participant ID number, and without any identifying information that would compromise the identity and confidentiality of the participants. Participant background information including name, gender, ethnicity, and relevant medical and personal information is kept in a centralized, restricted access location. This data handling system is efficient, guarantees confidentiality, and serves research needs expeditiously.

d. Study Conclusion

At the discretion of the protocol director, subjects may be taken out of this study due to unanticipated circumstances. Some possible reasons for withdrawing a subject from the study include: The subject fails to follow instructions or perform specified tasks; The investigator decides that continuation could be harmful to the subject; The subject requires treatment not allowed in the study; The study is cancelled; Other administrative reasons.

The experiment will terminate when all study procedures have been completed or when the participant withdraws from the study. Any Adverse Event will be immediately reported to the Stanford University IRB and the Psychiatry department chair.

e. Data Safety Monitoring Plan (DSMC)

i. Data and/or events subject to review

- Consent forms
- AEs, SAEs, SUSARs
- Protocol Deviations
- Progress toward Study endpoint(s)

All AEs will be reported to DSMB, NIMH, and/or IRB in compliance with NIMH Reportable Events Policy Schedule.

ii. Person(s) responsible for Data and Safety Monitoring

[name] (PI) and an independent monitoring committee

iii. Scope and Composition of Monitoring Board

The proposed data and safety monitoring board consists of senior and junior faculty with extensive experience in human subject research and/or clinical practice from

Stanford. DSMB members do not have any involvement and financial interests in the proposed study.

iv. Frequency of DSMB meetings

The DSMB will meet twice a year and will provide a written recommendation to NIMH after each meeting.

v. Specific triggers or stopping rules

We do not expect any AE or SAE associated with the proposed cognitive intervention and therefore we do not expect any stopping rule related to the intervention.

vi. DSMB Reporting

To PI and NIMH

vii. Will the Protocol Director be the only monitoring entity? (Y/N)

No

viii. Will a board, committee, or safety monitor be responsible for study monitoring? (Y/N)

Yes

f. Risks to Special Populations

N/A

7. BENEFITS

Participants may benefit indirectly through the information learned in their cognitive and behavioral evaluation as well as cognitive training. We believe this research will aid in the development of an efficient cognitive training method that can be ultimately used for boosting/restoring cognitive functions in individuals with impaired executive functioning.

8. PRIVACY AND CONFIDENTIALITY

All participant information and specimens are handled in compliance with the Health Insurance Portability and Accountability Act (HIPAA) and privacy policies of Stanford University, Stanford Health Care, and Stanford Children's Health.

A Novel Neuromonitoring Guided Cognitive Intervention for Targeted Enhancement of Working Memory

Statistical Analysis Plan

NCT04002167

August 25, 2023

The statistical analysis was computed in RStudio (R version 4.3.0) and the linear mixed-effect models for each behavioral dataset were constructed in lmer package to handle the missing data points. The analysis incorporated the interaction between group and session as a fixed effect, accounting for age, sex, and medication effects, while subject IDs were treated as a random effect in the model.

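### On the ordinary reading of the SAP's model each group gets its own baseline mean; a common-baseline mixed model would recover some precision, by an amount that depends on figures the documents do not give

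*SAP*

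**What the plan says.** The SAP is a single paragraph, and the protocol contains no analysis model.

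- **Fixed effects (SAP):** "The analysis incorporated the interaction between group and session as a fixed effect, accounting for age, sex, and medication effects".
- **Random effect (SAP):** "subject IDs were treated as a random effect in the model".
- **Scope and missing data (SAP):** "the linear mixed-effect models for each behavioral dataset were constructed in lmer package to handle the missing data points". The same model therefore serves every behavioural outcome, and missing scores are expected. Protocol section 5k also provides for children who leave early: "If the participant does not complete the all study visits".
- **Timing (SAP):** the past tense, "The statistical analysis was computed in RStudio".
- **Allocation (protocol section 2a, item 5):** "Participants will have 50% chance to undergo the cognitive training with neurofeedback"; the alternative is a waitlist.
- **Size (protocol section 5a):** "This research study is looking for 160 participants with ADHD".
- **Entry (protocol section 5h):** ADHD is "determined by a BRIEF Working Memory score" of at least 65.

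Neither document gives the model formula, the number or coding of sessions, which session is baseline, a pre-post correlation, or a dropout rate. Neither mentions the baseline score as a covariate or a baseline mean shared by the two groups.

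**The concern.** With session as a factor, the usual ways of writing a group-by-session interaction fit a separate baseline mean in each group. The tested effect is then the difference between groups in change from baseline. Under random allocation any baseline difference between groups is chance. Subtracting it in full, rather than in proportion to how well baseline predicts the later score, adds noise to the estimate.

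The listed covariates do not repair this. Taken as one value per child and entered as main effects, age, sex and medication are the same at every session and cancel from a within-child contrast. A reader could think that the adjustment had bought the usual precision gain when it had bought almost none.

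What is at stake is wider intervals and lower power on each behavioural outcome, recoverable from data the model already holds.

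**Working it through.** There is no power calculation or precision figure in the documents to reproduce.

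**Inputs.** From the documents: 160 children, equal allocation, so n = 80 per arm. Assumed: pre-post correlation rho of 0.5, 0.7 or 0.9; the model group*session + age + sex + medication + random intercept, with session as a factor; baseline SD s0 = 1; post SD s1 = 1 unless stated.

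**1. Complete data, equal variances.** The contrast variance is (2/n) × 2(1−rho) for the SAP model and (2/n) × (1−rho²) for the common-baseline model. The ratio is (1+rho)/2, so the reduction is (1−rho)/2.

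| rho | SAP variance (SE) | Common-baseline variance (SE) | Reduction | Share of 160 children |
|---|---|---|---|---|
| 0.5 | 0.02500 (0.158) | 0.01875 (0.137) | 25% | 40 |
| 0.7 | 0.01500 (0.122) | 0.01275 (0.113) | 15% | 24 |
| 0.9 | 0.00500 (0.071) | 0.00475 (0.069) | 5% | 8 |

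Exact generalised least squares gives the same reductions with 2, 3 or 4 sessions, if all sessions share one variance and one correlation. Assuming two-sided 5% tests, an effect with 80% power under the SAP model would have about 90%, 86% or 82%.

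**2. A fraction m of post scores missing (two sessions, no covariates).** The SAP variance is (2/n) × [(1−rho²)/(1−m) + (1−rho)²]; the common-baseline variance is (2/n) × (1−rho²)/(1−m). With m = 0.15 (assumed):

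- rho 0.5: 0.25 / (0.8824 + 0.25) = 22%
- rho 0.7: 0.09 / (0.6000 + 0.09) = 13%
- rho 0.9: 0.01 / (0.2235 + 0.01) = 4%

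**3. Unequal variances, complete data.** Var(change) = s1²(1−rho²) + (s0 − rho·s1)², and the first term is the baseline-adjusted variance. The excess is a square, so it cannot be negative. This is why the common-baseline contrast is never less precise in large samples.

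- s1 = 1.25: 0.1406/1.3125 = 11%; 0.0156/0.8125 = 2%; 0.0156/0.3125 = 5%
- s1 = 0.8: 0.3600/0.8400 = 43%; 0.1936/0.5200 = 37%; 0.0784/0.2000 = 39%

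**4. Baseline is the BRIEF entry score.** Assume that the cut lies 1.5 SD above the norm. The baseline variance left after selection is v = 0.1495, and Var(change) = (1−rho²) + v(1−rho)².

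- rho 0.5: 0.0374/0.7874 = 4.7%
- rho 0.7: 0.0135/0.5235 = 2.6%
- rho 0.9: 0.0015/0.1915 = 0.8%

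Here rho is the correlation in the unselected population. The loss is like 8, 4 or 1 of the 160 children.

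**5. Validity and covariates, by simulation.** Each setting had 1000 trials, 80 per arm, two sessions and a true effect of 0.40. Covariates were assumed to explain 12% of the variance.

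- Complete data: the SAP estimate with covariates, without covariates, and the plain change-score comparison agreed to 5 decimals in every trial.
- 15% of post scores missing completely at random: covariates moved the SAP estimate by only 0.011, 0.006 and 0.002 on average.
- 16% missing, depending on baseline and arm: the SAP model averaged 0.401, 0.398 and 0.396; the common-baseline model 0.400, 0.398 and 0.397. A complete-case change score averaged 0.260, 0.315 and 0.369.

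Both mixed models therefore hold where a complete-case change score would not.

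**The case against.** The strongest reply is that this is a choice between two valid analyses. A group-by-session mixed model is a standard method, it contradicts nothing in the protocol, and in the simulation it estimated the true effect. That stands. A reader might infer that the SAP ignores baseline or that its estimate is biased, and the documents support neither. If baseline is one of the sessions, the interaction already subtracts it, and the model keeps children with missing post scores.

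A second reply is that the separate baseline means are inferred. That also stands: no formula is given. An unusual coding, with session as a numeric 0/1 variable and no group main effect, would already be a common-baseline model. The point is therefore conditional, and stating the formula would settle it.

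A third is that 25% is a favourable figure. A reader might take it as the general loss. It needs complete data, equal variances and a correlation of 0.5, none of which the documents give. The only behavioural scale they name is the BRIEF, which is also the entry score and so gives the smallest gains; whether it is an outcome is not stated. Nor is the number of children analysed.

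A fourth is that the remedy needs facts not on the page. The protocol states a 50% chance but does not describe the randomisation, or say that baseline is measured before allocation. The order of procedures in section 2a suggests that it is, without settling it.

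Last, with no primary outcome named, a second model for every outcome adds analytic flexibility. Clear labelling limits this. None of these replies removes the gain in precision where the conditions hold.

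**Conclusion.** The point holds as an optional improvement in precision. On the ordinary reading, the SAP's contrast is valid under randomisation and missing at random, with the equal-variance form also needed where scores are missing. It is less precise than it could be, because it estimates a baseline mean in each group that randomisation makes common.

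The size depends on the outcome. For the three assumed correlations, the reduction falls a little when post scores are missing. It ranges from 2% to 43% when the post SD differs from the baseline SD by the amounts tried, and is below 5% if the baseline is the truncated entry score. Confidence is medium, because the correlation, the variance ratio, the sessions and the formula are all unstated. The case for a common baseline mean also rests on true randomisation with baseline measured first.

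**What to change.** 1. State the model formula, the sessions and their coding, and which session is baseline. Confirm that allocation was randomised and that baseline was measured before it.
2. For each behavioural dataset fit a common-baseline longitudinal mixed model: session as a factor, group terms only at post-baseline sessions, age, sex and pre-randomisation medication as covariates, unstructured within-child covariance, and REML with Kenward-Roger inference (for example in the mmrm package). Children with missing post scores stay in. ANCOVA on the baseline score can serve as a simple check.
3. If results are already known, report this as a labelled supplementary analysis beside the original model, not in its place.

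The cost is a few lines of code and, if results are known, a post hoc label. No new children or visits are needed. The small-sample correction matters: without it, common-baseline intervals covered 93.5% to 95.2% in the simulation, against 94.2% to 95.6% for the SAP model. For outcomes with a high pre-post correlation, or with the entry score as baseline, the gain may be too small to notice.

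### As time-fixed main effects, age, sex and medication barely touch the group-by-session contrast, so the adjustment the SAP describes hardly reaches the treatment effect

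*SAP*

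**What the plan says.** The SAP is two sentences long, and the second carries the model: it includes "the interaction between group and session as a fixed effect, accounting for age, sex, and medication effects", and "subject IDs were treated as a random effect in the model". The first sentence says the models "were constructed in lmer package to handle the missing data points", so some incomplete data are expected.

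The SAP does not give a model formula. It does not say whether the covariates enter as main effects only or also interact with session, whether medication is recorded once or at each session, or which contrast is the treatment effect.

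The protocol does not fill these gaps. Section 2.a, item 5, says "Participants will have 50% chance to undergo the cognitive training with neurofeedback", against a waitlist, and mentions no stratification. Section 5.a says "This research study is looking for 160 participants with ADHD". Section 5.b says "Participants (males and females) ages 7-11 years of all ethnic backgrounds will be recruited". The eligibility criteria in section 5.h do not restrict medication.

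**The concern.** The group-by-session term measures how much more one arm changes than the other. A child's age at entry, sex and baseline medication are the same at every session. As main effects they raise or lower all of a child's scores together, so they drop out of that child's change. A reader of the SAP would take the treatment effect to be adjusted for these three variables, when on the ordinary reading almost no adjustment reaches it.

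This matters if change itself depends on the covariates, for example if older children within the 7 to 11 range gain faster. A chance difference in age or medication between the arms then passes into the estimated effect, and variation in change that the covariates could explain stays in the error term.

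**Working it through.** **Inputs from the documents.** 160 children (protocol 5.a); 50% chance of training (2.a), taken as 80 per arm; ages 7 to 11 (5.b); group-by-session fixed effect, three covariates and a random subject effect (SAP). The documents state no figure that can be reproduced here.

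**Assumptions.** Two or three sessions; dropout 0 to 30%; random intercept only; interaction 0.4; covariate effects on level of 0.3 per year of age, 0.3 for sex and 0.4 for medication; subject SD 0.7 and residual SD 0.7. There were 100 simulated trials per setting, fitted by REML.

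**Step 1: algebra.** For child i at session j, write

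Y_ij = a + b·G_i + c_j + d_j·G_i + θ'X_i + u_i + e_ij,

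where X_i holds age, sex and medication, and session 1 is the reference. Then

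Y_i2 − Y_i1 = c_2 + d_2·G_i + (e_i2 − e_i1).

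Both θ'X_i and the random intercept u_i cancel. With complete data the estimate of d_2 is the difference between arms in mean change, with SE = √[2σ_e²(1/80 + 1/80)]. At σ_e = 0.7 this is √(0.98 × 0.025) = 0.157, and the simulated SE was also 0.157. No covariate appears in either expression.

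**Step 2: shift in the estimate when the three main effects are added, in SE units.**

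| Setting | 2 sessions: mean (largest) | 3 sessions: mean (largest) |
|---|---|---|
| Complete data, covariates balanced or imbalanced | 0 (0) | 0 (0) |
| 10% dropout | 0.06 (0.22) | 0.06 (0.17) |
| 20% dropout | 0.08 (0.36) | 0.07 (0.22) |
| 30% dropout | 0.11 (0.36) | 0.08 (0.25) |
| Complete data, 15% switch medication per session | 0.13 (0.46) | 0.14 (0.47) |

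In the first row the SE differed by less than 1e-8. With dropout and two sessions it fell by 0.3 to 0.8%. With medication switching it fell by 1.0 to 1.4%.

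**Step 3: when change depends on a covariate.** The change equation gains a term γ'X_i, and the main-effects model estimates d_2 + γ'(difference between arms in mean X). Age imbalance was built in to show the mechanism, with a true interaction of 0.40. With two sessions the mean estimates were 0.483 without covariates, 0.483 with main effects and 0.390 with covariate-by-session terms. With three sessions they were 0.515, 0.515 and 0.414. Main effects removed none of the imbalance; the session interactions removed nearly all of it.

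**Step 4: size under randomisation.** Assume slopes on change of 0.10 SD per year of age and 0.25 SD for medication, age uniform over 7 to 11, and half the children medicated.

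- Change variance explained: 0.10² × (11 − 7)²/12 + 0.25² × 0.25 = 0.0133 + 0.0156 = 0.029.
- Residual change variance at pre-post correlation r: 2(1 − r), which is 0.60 at r = 0.7.
- Cost of three extra terms: about 3/(160 − 6) = 1.9% of variance.
- Net variance ratio at r = 0.7: (0.60/0.629) × 1.019 = 0.972, a gain of about 3%. Simulation gave 3 to 4%.
- At r = 0.5: (1.00/1.029) × 1.019 = 0.990, a gain of about 1%. At r = 0.9: (0.20/0.229) × 1.019 = 0.890, a gain of about 11%.

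With stronger slopes as well, simulated gains reached 29%. With no dependence of change on the covariates, the extra terms cost about 1 to 2%. In simulation at r = 0.7, the estimate moved by 0.027 SD on average when the interactions were added (95th percentile 0.071 SD). Against an SE of about 0.129 that is 0.027/0.129 = 0.2 SE, and 0.071/0.129 = 0.55 SE.

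**The case against.** The strongest reply is that the SAP never says the covariates are main effects only. If covariate-by-session terms were fitted, the contrast is adjusted and one sentence settles the matter. That stands, and it is why the formula must be stated.

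A reader might infer that the three terms cannot change the estimate at all. The documents do not support that. The SAP itself expects missing data, and medication may vary by session; in both cases the estimate moves, as Step 2 shows. The movement is usually small and does not correct for change that depends on the covariates. Main effects also have a separate use: if dropout depends on age or medication, including them supports the missing-at-random assumption. They should stay in the model.

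The SAP does not name the tested contrast either. If it were the group difference at the last session, main effects would matter: in the imbalanced two-session setting that difference went from 0.661 (SE 0.175) to 0.409 (SE 0.161). The group-by-session term is the likelier target, being the only treatment term the SAP names.

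Finally, the SAP is written in the past tense, so a change of model now could be post hoc. That is a fair reason for a sensitivity label, but not for leaving the description as it is.

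**Conclusion.** The concern holds on the ordinary reading of the SAP. Time-fixed main effects leave the group-by-session estimate and SE exactly unchanged with complete data, and shift the estimate by about 0.1 SE on average with 10 to 30% dropout. The stated adjustment barely reaches the treatment contrast.

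It would be wrong to infer that the treatment effect is biased or the analysis invalid. With 1:1 randomisation the unadjusted change contrast is unbiased, and covariate adjustment is a choice. The loss is control of chance imbalance and a modest amount of precision: about 3 to 4% of variance under the assumed slopes at a correlation of 0.7, more with stronger slopes, and a loss of about 1 to 2% if the covariates are unrelated to change.

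The exact cancellation is algebra. The sizes rest on assumed slopes, correlation, number of sessions, dropout and medication switching, none of which the documents give.

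**What to change.** Write out the full model formula and name the tested contrast. Add the covariate-by-session terms:

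group\*session + age\*session + sex\*session + baseline medication\*session + (1 | subject)

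Report the group-by-session contrast from this model. If the primary analysis has already been run, report it as a labelled sensitivity analysis. State whether medication is the baseline value or is updated by session; the terms above need a baseline record. If only main effects are kept, do not describe the treatment contrast as adjusted for age, sex and medication.

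The cost is a short change to the SAP text and model code, about three degrees of freedom per added session, and up to about 2% of variance if the covariates turn out to be unrelated to change.
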